##### 8- Please indicate date and surgeon for your knee replacement operation

## OBJECTIVE KNEE INDICATORS (To be completed by surgeon)

### ALIGNMENT

#### 1- Alignment: measured on AP standing Xray (Anatomic Alignment)

25 point max

|                              |           |
|------------------------------|-----------|
| Neutral: 2-10 degrees valgus | (25 pts)  |
| Varus: < 2 degrees valgus    | (-10 pts) |
| Valgus: > 10 degrees valgus  | (-10 pts) |

### INSTABILITY

#### 2- Medial / Lateral Instability: measured in full extension

15 point max

|                  |          |
|------------------|----------|
| None             | (15 pts) |
| Little or < 5 mm | (10 pts) |
| Moderate or 5 mm | (5 pts)  |
| Severe or > 5 mm | (0 pts)  |

#### 3- Anterior / Posterior Instability: measured at 90 degrees

10 point max

|                 |          |
|-----------------|----------|
| None            | (10 pts) |
| Moderate < 5 mm | (5 pts)  |
| Severe > 5 mm   | (0 pts)  |

### JOINT MOTION

#### 4- Range of motion (1 point for each 5 degrees)

#### Deductions

Minus Points

|                            |           |
|----------------------------|-----------|
| Flexion Contracture |           |
| 1-5 degrees                | (-2 pts)  |
| 6-10 degrees               | (-5 pts)  |
| 11-15 degrees              | (-10 pts) |
| > 15 degrees               | (-15 pts) |

Minus Points

|                     |           |
|---------------------|-----------|
| Extensor Lag |           |
| <10 degrees         | (-5 pts)  |
| 10-20 degrees       | (-10 pts) |
| > 20 degrees        | (-15 pts) |

## SYMPTOMS

(To be completed by patient)

**Maximum total points (25 points)**

## PATIENT SATISFACTION

**Maximum total points (40 points)**

© 2011 by The Knee Society. All rights reserved. No part of this document may be reproduced or transmitted in any form or by any means, electronic, mechanical, photocopying, recording, or otherwise, without prior written permission of The Knee Society.

**PATIENT EXPECTATION** (To be completed by patient)**Compared to what you expected before your knee replacement:****1- My expectations for pain relief were... (5 points)**

- Too High- "I'm a lot worse than I thought" (1 pt)
- Too High- "I'm somewhat worse than I thought" (2 pts)
- Just Right- "My expectations were met" (3 pts)
- Too Low- "I'm somewhat better than I thought" (4 pts)
- Too Low- "I'm a lot better than I thought" (5 pts)

**2- My expectations for being able to do my normal activities of daily living were... (5 points)**

- Too High- "I'm a lot worse than I thought" (1 pt)
- Too High- "I'm somewhat worse than I thought" (2 pts)
- Just Right- "My expectations were met" (3 pts)
- Too Low- "I'm somewhat better than I thought" (4 pts)
- Too Low- "I'm a lot better than I thought" (5 pts)

**3- My expectations for being able to do my leisure, recreational or sports activities were... (5 points)**

- Too High- "I'm a lot worse than I thought" (1 pt)
- Too High- "I'm somewhat worse than I thought" (2 pts)
- Just Right- "My expectations were met" (3 pts)
- Too Low- "I'm somewhat better than I thought" (4 pts)
- Too Low- "I'm a lot better than I thought" (5 pts)

**Maximum total points (15 points)**

**STANDARD ACTIVITIES (30 points)**

How much does your knee bother you during each of the following activities?

| no bother | moderate | very severe | cannot do (because of knee) | I never do this |   |
|-----------|----------|-------------|-----------------------------|-----------------|---|
| 5         | 4        | 3           | 2                           | 1               | 0 |

1 - Walking on an uneven surface

|                       |                       |                       |                       |                       |                       |                       |                       |
|-----------------------|-----------------------|-----------------------|-----------------------|-----------------------|-----------------------|-----------------------|-----------------------|
|  |
|-----------------------|-----------------------|-----------------------|-----------------------|-----------------------|-----------------------|-----------------------|-----------------------|

2 - Turning or pivoting on your leg

|                       |                       |                       |                       |                       |                       |                       |                       |
|-----------------------|-----------------------|-----------------------|-----------------------|-----------------------|-----------------------|-----------------------|-----------------------|
|  |
|-----------------------|-----------------------|-----------------------|-----------------------|-----------------------|-----------------------|-----------------------|-----------------------|

3 - Climbing up or down a flight of stairs

|                       |                       |                       |                       |                       |                       |                       |                       |
|-----------------------|-----------------------|-----------------------|-----------------------|-----------------------|-----------------------|-----------------------|-----------------------|
|  |
|-----------------------|-----------------------|-----------------------|-----------------------|-----------------------|-----------------------|-----------------------|-----------------------|

4 - Getting up from a low couch or a chair without arms

|                       |                       |                       |                       |                       |                       |                       |                       |
|-----------------------|-----------------------|-----------------------|-----------------------|-----------------------|-----------------------|-----------------------|-----------------------|
|  |
|-----------------------|-----------------------|-----------------------|-----------------------|-----------------------|-----------------------|-----------------------|-----------------------|

5 - Getting into or out of a car

|                       |                       |                       |                       |                       |                       |                       |                       |
|-----------------------|-----------------------|-----------------------|-----------------------|-----------------------|-----------------------|-----------------------|-----------------------|
|  |
|-----------------------|-----------------------|-----------------------|-----------------------|-----------------------|-----------------------|-----------------------|-----------------------|

6 - Moving laterally (stepping to the side)

|                       |                       |                       |                       |                       |                       |                       |                       |
|-----------------------|-----------------------|-----------------------|-----------------------|-----------------------|-----------------------|-----------------------|-----------------------|
|  |
|-----------------------|-----------------------|-----------------------|-----------------------|-----------------------|-----------------------|-----------------------|-----------------------|

Maximum points (30 points)

|                       |
|-----------------------|
|  |
|-----------------------|

**ADVANCED ACTIVITIES (25 points)**

1 - Climbing a ladder or step stool

|                       |                       |                       |                       |                       |                       |                       |                       |
|-----------------------|-----------------------|-----------------------|-----------------------|-----------------------|-----------------------|-----------------------|-----------------------|
|  |
|-----------------------|-----------------------|-----------------------|-----------------------|-----------------------|-----------------------|-----------------------|-----------------------|

2 - Carrying a shopping bag for a block

|                       |                       |                       |                       |                       |                       |                       |                       |
|-----------------------|-----------------------|-----------------------|-----------------------|-----------------------|-----------------------|-----------------------|-----------------------|
|  |
|-----------------------|-----------------------|-----------------------|-----------------------|-----------------------|-----------------------|-----------------------|-----------------------|

3 - Squatting

|                       |                       |                       |                       |                       |                       |                       |                       |
|-----------------------|-----------------------|-----------------------|-----------------------|-----------------------|-----------------------|-----------------------|-----------------------|
|  |
|-----------------------|-----------------------|-----------------------|-----------------------|-----------------------|-----------------------|-----------------------|-----------------------|

4 - Kneeling

|                       |                       |                       |                       |                       |                       |                       |                       |
|-----------------------|-----------------------|-----------------------|-----------------------|-----------------------|-----------------------|-----------------------|-----------------------|
|  |
|-----------------------|-----------------------|-----------------------|-----------------------|-----------------------|-----------------------|-----------------------|-----------------------|

5 - Running

|                       |                       |                       |                       |                       |                       |                       |                       |
|-----------------------|-----------------------|-----------------------|-----------------------|-----------------------|-----------------------|-----------------------|-----------------------|
|  |
|-----------------------|-----------------------|-----------------------|-----------------------|-----------------------|-----------------------|-----------------------|-----------------------|

Maximum points (25 points)

|                       |
|-----------------------|
|  |
|-----------------------|

© 2011 by The Knee Society. All rights reserved. No part of this document may be reproduced or transmitted in any form or by any means, electronic, mechanical, photocopying, recording, or otherwise, without prior written permission of The Knee Society.

## DISCRETIONARY KNEE ACTIVITIES (15 points)

Please check 3 of the activities below that you consider *most important* to you.

(Please do not write in additional activities)

## Recreational Activities

- Swimming
- Golfing (18 holes)
- Road Cycling (>30mins)
- Gardening
- Bowling
- Racquet Sports (Tennis, Racquetball, etc.)
- Distance Walking
- Dancing / Ballet
- Stretching Exercises (stretching out your muscles)

## Workout and Gym Activities

- Weight-lifting
- Leg Extensions
- Stair-Climber
- Stationary Biking / Spinning
- Leg Press
- Jogging
- Elliptical Trainer
- Aerobic Exercises

Please copy all 3 checked activities into the empty boxes below.

How much does your knee bother you during each of these activities?

Activity  
(Please write the 3 activities  
from list above)

| no
bother | slight | moderate | severe | very
severe | cannot do
(because
of knee) |
|--------------|--------|----------|--------|----------------|-----------------------------------|
| 5            | 4      | 3        | 2      | 1              | 0                                 |

1.

     

2.

     

3.

     

Maximum points (15 points)

Maximum total points (100 points)

© 2011 by The Knee Society. All rights reserved. No part of this document may be reproduced or transmitted in any form or by any means, electronic, mechanical, photocopying, recording, or otherwise, without prior written permission of The Knee Society.

## DATA ANALYSIS

Once the subjects have completed the activity, the fluoroscopic videos will be stored digitally and specific frames of interest will be captured from the video and exported into the preprocessing software. The specific frames of interest will be full extension, maximum knee flexion (both inclusive), and 30° knee flexion increments during the complete flexion cycle.

Our 3D to 2D registration technique will be used to overlay the 3D models of the implanted components on their projection in the 2D fluoroscopic image. The fluoroscopic video would be digitized into frames and corrected for distortion. From here, the distortion-free images would be used with the 3D to 2D registration technique to extract in vivo patient femorotibial kinematics, which involves overlaying the 3D models of the components on their projection in the 2D fluoroscopic image.

Statistical analysis of the data will be carried out to analyze the two cohorts. All variables, except for lift-off and VAG, will be denoted as continuous. The data will be first checked for normality using the Shapiro-Wilk test. Only when the data is found to be normally distributed will parametric tests be used; otherwise, non-parametric tests will be used. The data will also be tested for equality of variance using the Barlett's test and Levene's test. The final selection criterion for the type of test to conduct will be based on the check for normality, as well as the check for equal variance. Therefore, for all the continuous variables, the following tests will be used:

1. Student's t-test (when the data is normally distributed and has equal variance).
2. Welch Anova test (when the data is normally distributed but has unequal variance).
3. Wilcoxon Mann Whitney U-test (when the data is not normally distributed).

Lift-off, as applicable, will be treated as a categorical variable in this study and a contingency analysis using the Fisher's exact test will be carried out. All statistical tests will be carried out at 95% confidence level ( $\alpha=0.05$ ) and will be performed using JMP® Statistical Discovery™ (SAS Institute Inc., Cary, NC) software.

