## ***Introduction:***

A better understanding of knee joint kinematics is important to explain the premature polyethylene wear failures, patient dissatisfaction with function and to help design a prosthesis that most closely approximates the normal knee. Previously, most experimental studies of knee kinematics have involved cadaveric, in vitro analyses, or have not tested the knee in a weight-bearing mode. Others have used exoskeletal linkages and skin markers that permit error due to undesired motions between markers and the underlying bone. More recently, fluoroscopy has been used to assess in vivo kinematics for subjects having a TKA. These in vivo studies have defined the following abnormal kinematic patterns that exist with total knee arthroplasty (TKA), in comparison to the normal knee:

1. Most subjects having a posterior cruciate retaining PCR TKA and some having a posterior stabilized (PS) TKA experience a paradoxical translational of the femoral component relative to the tibial component
2. All TKA types experienced a significant percentage of subjects having reverse axial rotation, where the femoral component internally rotates with increasing knee flexion, opposite of the normal knee.
3. All TKA types demonstrate the occurrence of condylar lift-off, where one condyle raises off the tibial plateau.

New TKA continue to be designed and marketed to the patient and surgeon, but are these designs significantly different than those previously offered? What is the rational for those design changes and do they truly offer an advantage? More recently, Zimmer-Biomet brought a new knee implant to the orthopaedic market, called the Persona TKA. This family of TKA includes both a posterior stabilized and posterior cruciate retaining design for the surgeon to choose. More recently, surgeons have implanted both the PCR and PS Persona TKA into patients, but as of today Zimmer does not have in vivo data validating their design or have compared the kinematic results with those patients previously evaluated having either a NexGen PCR or PS TKA. Therefore, the objective for this study is to analyze the in vivo kinematics for patients implanted by two surgeons having either a Zimmer-Biomet Persona PCR or PS TKA.

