## ***Hypothesis:***

1. It is hypothesized that subjects having a PS TKA will experience greater posterior femoral rollback, axial rotation and weight-bearing flexion than subjects having a PCR TKA.
2. It is hypothesized that subjects having a Persona TKA will experience better kinematic patterns than subjects previously analyzed having a NexGen TKA.

***Study design:*** In vivo knee kinematics will be assessed for 25 subjects that have been implanted with a Zimmer-Biomet Persona fixed bearing posterior stabilizing (PS) total knee arthroplasty (TKA) by [name] [name] of the Institute for Locomotion, Aix-Marseille University, Hopital Sainte-Marguerite. The other 25 subjects with the Zimmer-Biomet Persona fixed bearing poster cruciate retaining (PCR) TKA will be provided by another surgeon at a separate site, which has yet to be determined. [name] and [name] both of the Institute for Locomotion, Aix-Marseille University, Hopital Sainte-Marguerite will serve as Sub-Investigators. [name] of the University of Tennessee will also serve as a Sub-Investigator. Enrollment will be increased to 28 subjects per implant type to ensure that researchers acquire the necessary 25 usable datasets for analysis for each implant type and also

to account for any subjects that may drop out of the study. All TKAs should be judged clinically successful (KSS > 75). Each subject should have a well-functioning prosthesis, be at least six months post-operative, and should have good-to-excellent post-operative passive flexion.

Deciding which subjects received which kind of implant was up to the discretion of the study surgeon, according to his professional opinion. The determination as to which type of implant subjects received is outside the scope of this particular study. Subjects will already have the knee implants and must be at least six months post-operative.

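### Does letting a normality check choose between a mean test and a rank test undermine the PS versus PCR comparison in Hypothesis 1?

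*SAP*

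**What the plan says.** Hypothesis 1 in the Protocol is directional but names no parameter: "subjects having a PS TKA will experience greater posterior femoral rollback, axial rotation and weight-bearing flexion than subjects having a PCR TKA". It does not say whether the comparison is of means, of medians, or of the chance that a PS knee exceeds a PCR knee.

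The SAP (Data Analysis) sets the choice of test by pre-testing: "Only when the data is found to be normally distributed will parametric tests be used; otherwise, non-parametric tests will be used". Variance is checked too: "The data will also be tested for equality of variance using the Barlett's test and Levene's test". The final choice "will be based on the check for normality, as well as the check for equal variance". Three tests follow:

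- Student's t for normal data with equal variance
- Welch for normal data with unequal variance
- Mann-Whitney for non-normal data

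On measurement points the SAP says: "The specific frames of interest will be full extension, maximum knee flexion (both inclusive), and 30° knee flexion increments". It applies the test rule to the continuous variables in general and does not say that the rule is run afresh at each frame. Nor does it say whether normality is checked within each implant group, on pooled data or on residuals, or what happens if Bartlett and Levene disagree.

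**The concern.** The t and Welch tests compare means. Mann-Whitney in general does not, so the quantity tested depends on the Shapiro-Wilk result. Kinematic data are captured at several flexion angles. If the rule ran at each angle, one variable such as rollback could be compared by means at 30 degrees and by ranks at 60 degrees. The p-values along the curve would then share no effect measure in mm or degrees.

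A second worry is error control. If the intended target is the mean difference, a rank test can reject too often when skewed data also have unequal spread. Differing distribution shapes are not far-fetched, since the Protocol's Introduction reports that "Most subjects having a posterior cruciate retaining PCR TKA and some having a posterior stabilized (PS) TKA experience a paradoxical translational". The cure also looks cheap, because Welch and Mann-Whitney are already in the plan.

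**Working it through.** **Inputs.** The level is 0.05 (SAP: "All statistical tests will be carried out at 95% confidence level"), taken to cover Shapiro-Wilk as well. There are 25 usable datasets per implant type (Protocol, Study design). The number of frames is not stated: 0, 30, 60, 90 degrees and maximum make five if maximum flexion is above 90 and up to 120 degrees, four if it is above 60 and up to 90, and six above 120. Between-frame correlation is not given; 0 to 0.95 is assumed. The plan states no power, effect size or SD, so it has no figure to reproduce.

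**1. How often would test types mix across frames, on normal data?** With independent frames, P(mixed) = 1 - (1-q)^K - q^K, where q is the chance that a frame goes to the rank test.

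- Checked in each group: q = 1 - 0.95² = 0.0975. K = 5 gives 1 - 0.9025^5 - 0.0975^5 = 40.1%; K = 4 gives 33.7%; K = 6 gives 46.0%.
- One check on residuals: q = 0.05. K = 5 gives 1 - 0.95^5 - 0.05^5 = 22.6%.

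Simulation with correlated frames (five frames, 25 per group) lowers these. By group, the rate is 28.5-31.2% at correlation 0.9 and 23.6-29.4% at 0.95. On residuals it is 15.6-17.8% and 11.7-14.2%. The five-frame range is therefore about 12-41%. A variable with one value per subject, such as maximum weight-bearing flexion, cannot mix at all.

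**2. Does mixing matter on those data?** For two normal groups, P(PS > PCR) = Φ((μ₁-μ₂)/√(σ₁²+σ₂²)), which equals 0.5 exactly when the means are equal. Mean and rank tests then share the same null and direction. Comparing the SAP rule with Welch throughout on the same normal, equal-variance samples, the verdict at 0.05 differs in 0.5% (no effect), 1.1% (0.5 SD) and 0.8% (0.8 SD). Across runs the range is 0.3-1.1%.

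**3. Error for a mean difference (simulated, equal means).**

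| Data | SAP rule | Welch |
|---|---|---|
| Gamma shape 2, SD ratio 1 (identical) | 4.9% | 4.8% |
| Gamma shape 2, SD ratio 1.5 | 9.2% | 5.2% |
| Gamma shape 2, SD ratio 2 | 12.4% | 5.8% |
| Gamma shape 2, SD ratio 3 | 17.3% | 6.2% |
| Mixtures in both arms, shifts of 2-3 SD | 4.7-7.3% | 4.4-5.6% |

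The gamma shape and the SD ratios are assumptions. The mixtures imitate the Introduction's pattern, with assumed PCR/PS shares of 60/25, 60/40, 70/30 and 75/25. At a 5 SD shift the SAP rule gives 5.6-7.2% for the first three shares and 12.6% for 75/25.

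**4. Power at a 0.8 SD shift.**

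| Data | SAP rule | Welch | Mann-Whitney |
|---|---|---|---|
| Normal | 78.7% | 78.8% | 75.9% |
| Gamma shape 2 | 87.4% | 78.5% | 87.5% |
| t, 3 df | 93.8% | 83.6% | 94.6% |

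The rule falls short of the better fixed test by 0.1, 0.1 and 0.8 points. Relative to the rule, Welch throughout loses 8.9 and 10.2 points in the last two rows; Mann-Whitney throughout loses 2.8 points under normality.

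**5. Unspecified details.** Varying the normality unit (group, pooled, residual) and the variance test changes which test is chosen in about 10-30% of normal or gamma samples. The verdict changes in only about 0.4-2.5%. The three listed tests cover every outcome: variance separates the first two, and non-normality leads to the third. No branch is missing.

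**The case for a change.** The best case for a change is that a plan should say what it estimates before it picks a test. Here no target, effect measure or interval is named, so a significant rank result could not be reported as a difference in mm or degrees. Real data need not be normal. With mild skew (gamma shape 8), mixing across five frames would rise to 58-88%. On the same samples, Welch and Mann-Whitney disagree in 2% with no effect, 7% at a 0.5 SD normal shift and 14% at a 0.5 SD shift of gamma shape 2. The remedy costs only wording.

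Part of this stands. The target is indeed unnamed, and stating it would make the report easier to read. The frame-by-frame reading is reasonable, though the SAP does not state it. However, the disagreement under a pure shift reflects unequal power rather than opposing answers, and there the rank branch is the stronger test. The kinematic curves described in the Protocol's Data Collection section come from the measurements, so group differences can be plotted in mm and degrees whichever test is used. Fixing one test gives something up in either direction, so the remedy is a preference among sound options.

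**Conclusion.** No change follows. Naming the parameter, the normality unit and the Bartlett-versus-Levene rule is missing detail that a competent analyst supplies when reporting; the last two alter the verdict in roughly 0.4-2.5% of samples. Replacing the rule by one fixed test is a trade-off: the rule holds about 5% under identical distributions and keeps within 1 point of the better test's power in the three settings above, whereas Welch throughout would give up about 9-10 points in two of them.

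The 12-41% mixing figure is correct under its assumptions (rule applied per frame, five frames, normal data, correlation up to 0.95), but it counts changes of test type, not changed conclusions. The inflated error of 9-17% requires strong skew together with SD ratios of 1.5-3 and a mean-difference target. Nothing in the documents supports those values, and the scenario closest to the Introduction stays at 4.7-7.3% unless the shift is extreme.
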